1.0 Research Design

1.1 Purpose/Specific Aims

A. Objectives

The objective of this study is to compare surgeons' discernment of 4 balloons filled with different materials when using their eyes and hands versus using the da Vinci robot.

B. Hypotheses / Research Question(s):

We believe that so called "visual haptics" derived from the high definition 3D optics associated with robotic surgery will allow for non-inferior object discernment compared to actual haptics of touching objects with surgeons' hands.

1.2 Research Significance (Briefly describe the following in 500 words or less)

Robotic surgery has emerged as a transformative technology in the field of medicine, revolutionizing surgical procedures across various specialties. The integration of advanced robotic systems, such as the da Vinci Surgical Systems, has provided surgeons with enhanced precision, improved dexterity, and greater visualization during complex surgical interventions. These advancements have been realized despite the lack of haptic feedback to the surgeon when using the da Vinci systems.

Robotic-assisted surgery is typically done through small incisions through which the surgeon places access points (ports) which are then connected to the robotic arms. The robotic arms hold the specialized robotic instruments and the high-definition 3D camera. After setting everything up, the surgeon sits at a console near the operating table and views the magnified, high-resolution 3D image of the surgical site. The surgeon's fingers are inserted into master controls on the console, which are designed to mimic the movements of the surgeon's hands. **Figure 1** depicts the most widely used robotic system – the da Vinci System (Intuitive Surgical, Sunnyvale CA) versus traditional laparoscopy.

Haptic feedback (i.e. the sense of touch) helps surgeons perceive the texture, resistance and consistency of various tissues and structures. This information helps surgeons maintain the optimal force during tissue manipulation. Ever since the first use of the da Vinci system in 1999, critics have bemoaned the lack of haptics as the Achilles heel of robotic surgery.

However, experienced robotic surgeons often report that they develop the sense of “visual haptics” that allows them to discern various properties of different tissue types as though they could actually feel them simply through a combination of manipulation and visualization.

To date, no studies have compared surgeons’ ability to discern the nature of objects with their hands to robotic surgeons’ ability to discern them while using only the robotic technology.

1.3 Research Design and Methods

A. Research Procedures

This will be a non-randomized parallel group study in which a group of surgeons (Group A) will make determinations as to the material within each of four visually identical balloons that contain air, water, petroleum jelly or a firm substance similar to the consistency of a non-ripe banana (Figure 2) using their hands and eyes while another group of experienced robotic surgeons (Group B) will do so using the da Vinci Xi System (Intuitive Surgical, Sunnyvale, CA). Only Board-certified surgeons will be recruited for the study. The study information will be obtained at Valley Hospital and the Intuitive Surgical training facility in Atlanta, Georgia.

Surgeon demographics will be recorded on Case Report Form #1

Before making their “hands on” determinations as to balloon contents, each surgeon will be asked to first determine whether they can visually determine the balloon contents without any manipulation. For the purposes of outcome measurement, only two possible outcomes will be considered – namely that the 4 balloons were ordered correctly or not. We will also record each “guess” for all surgeons in order to report any trends of mis-assortment that may occur.

B. Duration for Study and Each Subject

Each study participant will spend about 5 minutes doing study activities. We estimate that we will be finished with data collection by September 1st, 2023

All data collection will be performed by [name]

1.3 Preliminary Data

Our balloon model was informally deemed plausible by myself and two other colleagues. (Figure 1)

1.4 Sample Size Justification

The probability of ordering all balloons correctly by chance is 1/24 or .0417.

The expectation is that group A will achieve 100% success. If so, we will require **35 surgeons in Group A and 18 surgeons in Group B** to achieve 80% power to make the determination that Group B was (or was not) “non-inferior” at discerning balloons (alpha = 0.05).

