1.6 Study Variables

A. Independent Variables, Interventions, or Predictor Variables

Primary outcome: (y/n) whether balloons were sorted correctly

Secondary outcome: Trends for any mis-assignments of balloons

De-identified surgeon demographics will be compared between groups

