5.0 Data Management Plan

5.1 Data Analysis

Continuous variables will be compared via T-tests or Mann-Whitney test as applicable; Categorical data will be compared via chi square test. Power calculation / sample size estimate information as above.

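### The 80% power for the non-inferiority decision cannot be derived, because no margin, Group B rate or sidedness is given, and the only categorical test named is chi-square

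*Protocol*

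**What the plan says.** The study has one hypothesis (section 1.1): that robotic visual haptics "will allow for non-inferior object discernment compared to actual haptics" of the hand. No margin is attached to it.

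Section 1.4 gives the chance rate ("The probability of ordering all balloons correctly by chance is 1/24 or .0417"), an assumption for Group A ("The expectation is that group A will achieve 100% success"), the sizes ("35 surgeons in Group A and 18 surgeons in Group B"), and the claim that these suffice "to achieve 80% power to make the determination that Group B was (or was not") non-inferior "at discerning balloons (alpha = 0.05"). The chance rate is not linked to the power claim.

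Section 1.6 defines a binary endpoint: "Primary outcome: (y/n) whether balloons were sorted correctly". Section 5.1 supplies the analysis: "Categorical data will be compared via chi square test. Power calculation / sample size estimate information as above". That adds no input to section 1.4 and names no non-inferiority test or confidence bound. As written, its sentence on categorical data covers the binary primary outcome.

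**The concern.** Non-inferiority power depends on the margin, the true rate in each group, the one-sided alpha, the sample sizes and the decision rule. Section 1.4 fixes the sizes, the Group A rate and an alpha of unstated sidedness, and leaves the rest open. The 80% therefore cannot be recomputed by a reader.

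The protocol also contains no rule that could decide its only hypothesis. A chi-square test asks whether the groups differ, and with 18 surgeons in one group a non-significant result is compatible with a large deficit. If the margin is chosen after the data are seen, one surgeon's result can turn the conclusion either way. The two-way wording (was, or was not) adds a further problem: failing to show non-inferiority does not establish inferiority, so one power figure cannot cover both outcomes.

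**Working it through.** **Inputs from the protocol.** nA = 35, nB = 18, Group A rate 100%, alpha 0.05, power 80% (all section 1.4). **Assumptions of this check, because the protocol is silent:** margins of 10 to 30 points, Group B rates of 80% to 99%, alpha one-sided 5% or 2.5%.

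**1. Trying to reproduce 80%.** From the stated inputs alone it cannot be done. If both groups are set at 100%, the Wald variance is zero and the formula degenerates. Different unstated inputs do return 35 and 18:

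- Difference test, one-sided 5%, 100% v 80%, pooled variance. Pooled rate = (35 + 18×0.8)/53 = 0.932. SE under the null = √(0.932×0.068×(1/35 + 1/18)) = 0.0730. SE under the alternative = √(0.8×0.2/18) = 0.0943. Power = Φ((0.20 − 1.645×0.0730)/0.0943) = 80.2%.
- Non-inferiority, Wald, margin 30 points, Group B 90%, one-sided 2.5%. SE = √(0.9×0.1/18) = 0.0707. Power = Φ((0.30 − 0.10)/0.0707 − 1.960) = 80.7%.

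These answer different questions, so the basis of the sample size is not identified.

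**2. What each Group B result would show.** Lower bounds for B minus A, in points, with Group A at 35/35 (one-sided 5% / 2.5%):

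| Group B | Score (Miettinen-Nurminen) | Newcombe | Wald |
|---|---|---|---|
| 18/18 | −13.3 / −17.9 | −13.1 / −17.6 | 0 / 0 (zero variance) |
| 17/18 | −21.7 / −26.0 | −21.5 / −25.8 | −14.4 / −16.1 |
| 16/18 | −28.8 / −33.0 | −28.6 / −32.8 | −23.3 / −25.6 |

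Exact unconditional one-sided p-values agree with the score and Newcombe decisions at 20 and 25 points. For 20 points they are 0.021 (18/18) and 0.099 (17/18). For 25 points they are 0.010 (18/18), 0.040 (17/18) and 0.135 (16/18).

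**3. Power.** If at least k of 18 are required, power = P(Bin(18, pB) ≥ k).

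| Required | pB 99% | 95% | 90% | pB needed for 80% power |
|---|---|---|---|---|
| 18/18 | 83% | 40% | 15% | 98.8% |
| 17/18 | 99% | 77% | 45% | 95.4% |
| 16/18 | 99.9% | 94% | 73% | 91.4% |

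By the score or Newcombe bound, the margins lead to these requirements:

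- 10 points: not attainable even with 18/18, at either alpha.
- 20 points: 18/18 at either alpha.
- 25 points: 17/18 at one-sided 5%, 18/18 at one-sided 2.5%.
- 30 points: 16/18 at one-sided 5%, 17/18 at one-sided 2.5%.

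**4. The named test.** Uncorrected chi-square with Group A at 35/35:

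- 17/18: 53×(35×1)²/(35×18×52×1) = 1.98, p = 0.16. The smallest expected count is 18×1/53 = 0.34.
- 16/18: 53×(35×2)²/(35×18×51×2) = 4.04, p = 0.044.
- 18/18: no failures in either group, so expected failures are zero and the statistic cannot be computed.

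So 17/18 is not significant, although its score bound allows a deficit of 21.7 points (one-sided 5%) or 26.0 points (one-sided 2.5%).

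**5. False passes.** A rule that accepts 17/18 or better passes a Group B with a true rate of 80% with probability 18×0.8¹⁷×0.2 + 0.8¹⁸ = 0.081 + 0.018 = 9.9%, and one with a true rate of 85% with probability 22%. Requiring 18/18 gives 1.8% at 80%. The 17/18 rule is what a Wald bound implies at 20 points. It is also what results from reading a non-significant uncorrected chi-square as non-inferior (counting 18/18 as a pass).

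**The case against.** The strongest reply is that nothing is shown to be miscalculated. Unstated inputs reproduce 35 and 18 with about 80% power, including a genuine non-inferiority calculation at a 30-point margin, so the figure may come from a proper calculation that was not written out. That stands, and it is why the 80% is called unsupported and not wrong. It does not repair the statement: a difference test fits equally well, and a reader cannot tell which was meant.

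Second, analysis detail may sit in an SAP that is not shown, and section 5.1 is a generic sentence that does not say a non-significant chi-square will be read as non-inferiority. Both are fair. The choice between score and exact bounds can be left to an SAP. But the protocol itself asserts a power figure for a non-inferiority decision, and the only test that it names for a yes/no outcome cannot make that decision.

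Third, the illustrations depend on choices. The power figures change greatly with the margin, as the range above shows. The chi-square illustration holds for the uncorrected test. With continuity correction 16/18 gives p = 0.21, and Fisher's test gives 0.11, so those versions would leave even 16/18 non-significant. This makes reliance on a non-significant result more lenient, not less.

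Finally, this is a short bench task without patients. That limits the harm but not the effect on the conclusion.

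**Conclusion.** The concern holds. The protocol gives no margin, Group B rate or sidedness, so the 80% in section 1.4 cannot be derived, and the test in section 5.1 cannot decide the only hypothesis.

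The effect is large enough to reverse the result. At one-sided 5%, 17/18 fails a 20-point margin and meets a 25-point one under the score, Newcombe and exact unconditional methods. At a true Group B rate of 95%, power with the same 53 surgeons is 40% for 20 points and 77% for 25 points. A Wald bound would differ, passing 17/18 at 20 points at either alpha, but at the cost of the 9.9% false-pass rate at a true rate of 80%.

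All of this assumes Group A scores 35/35, as section 1.4 expects. The margins and Group B rates are illustrations and are not recommendations.

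**What to change.** Before any results are seen:

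1. In section 1.4, state the margin and the reason for it, the one-sided alpha, and the assumed Group A and Group B rates. Replace the 80% with the power that 35 and 18 give under those inputs and the rule in section 5.1.
2. In section 5.1, judge the primary outcome by a lower confidence bound (score or exact) for B minus A against that margin. Keep chi-square for the other categorical comparisons.
3. Reword the two-way phrase so that power refers only to concluding non-inferiority.

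Suggested text:

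> Non-inferiority is concluded if the lower one-sided [95 or 97.5]% [score or exact] bound for the success rate in B minus A is above −[margin]. If Group A is 35/35 this requires at least [x]/18; power is [y]% if the true Group B rate is [z]%. If the bound is not above −[margin], non-inferiority was not shown.

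The cost is wording in two sections, with no change in procedures and no extra surgeons, provided the justified margin is attainable with 35 and 18. A 10-point margin is not attainable by the score or Newcombe bound, and the sizes would then need to be revisited. The restated power may also be less favourable than 80%.

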1.6 Study Variables

A. Independent Variables, Interventions, or Predictor Variables

Primary outcome: (y/n) whether balloons were sorted correctly

Secondary outcome: Trends for any mis-assignments of balloons

De-identified surgeon demographics will be compared between groups

1.7 Data Collection

A. Primary Data Collection

- **Location:** The Valley Hospital and Intuitive Surgical Training Center in Atlanta GA. (Permission to conduct study at the Intuitive Surgical site obtained from [name] , Intuitive Surgical CMO.
- **Process of Data Collection:** Case Report Forms (see attached) will be filled out and collected by [name]
- **Timing and Frequency:** One time only per surgeon. Data collection will happen in 1 or 2 days at the Intuitive Surgical site – dates TBD
- **Procedures for Audio/Visual Recording:** N/A
- **Study Instruments:** The balloon model (Figure 2) is made of posterboard to which 4 balloons (Party City gold 5 inch) each containing 20 mL of material – either air, water, petroleum jelly, or water-absorbing crystals (LiquiLock, Oatey Inc) are affixed (Figure 1) The same model will be used for all data collection if possible, but in the event of balloon breakage or some other reason, identical replacement balloons may be created easily. The surgeons will be allowed to manipulate the balloons with their hands (Group A) or the robotic instruments (Group B) as they see fit, but they must leave the poster board laying flat with the balloons still attached. Surgeon Demographics (de-identified) and study data will be collected on Case Report forms 1 & 2. (Figures 3 & 4)
- **Ethnographic Studies, Interviews, Or Observation:** Surgeons will be allowed to manipulate the balloons as they see fit whether they are using their hands or the robotic instruments, but they will not be allowed to disconnect the balloons from the poster board. The poster board must lay flat at all times.

- **Subject Identifiers:** [name] will hold the key indicating which substance is in each balloon. Each surgeon will be assigned a subject number sequentially.

B. Secondary Data Collection

N/A

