3.0 Multi Center Research N/A

4.0 Research Data Source/s

4.1 Subject Selection and Enrollment Considerations

A. Method to Identify Potential Subjects

For the non-robotic surgeons, we will use any Board Certified surgeons on staff at The Valley Hospital. For the robotic surgeons, we will use any The Valley Hospital surgeons with unrestricted robotic privileges or any similarly credentialed robotic surgeons we encounter at the Intuitive Surgical Training Center.

B. Recruitment Details –

[name] will approach surgeons to ask for their participation and guide them through the study process

C. Subject Screening –

Surgeons will review the below criteria and self-select whether they are eligible

- **Inclusion Criteria –**
Group A (35 surgeons) Board Certified surgeons
Group B (18 surgeons) Board Certified surgeons with unrestricted robotic privileges
- **Exclusion Criteria –** Surgeons unwilling to spend adequate time to participate in the study or those who are not Board Certified

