4.4 Consent Procedures

A. Consent Process

- **Location of Consent Process**
In lieu of signing traditional informed consent, each surgeon will be provided with a Study Information Sheet. Their participation in the study will serve as implied informed consent.
- **Consent Discussion Duration**
5 minutes or less
- **Coercion or Undue Influence**
N/A
- **Subject Understanding**
Their participation will imply their understanding

B. Waiver or Alteration of Consent Process

▪ **Waiver or Alteration Details**

This study does not involve any patient care or any other risky situations. In fact, this study carries the smallest possible risks to the study subjects. At the same time, the surgeons who agree to be subjects are very busy people. Keeping the enrollment process to a minimum will be critical for obtaining participation.

- **Destruction of Identifiers**
No Identifiers will be collected (see Figure 3)
- **Use of Deception/Concealment**
N/A
 - a. **Minimal Risk Justification**
No patient care of any kind will be included in the study. The only study activity will be manipulation of inanimate objects.
 - b. **Alternatives**
Use of human or animal tissue is not practical, because the study design calls for uniformity of the model objects. The materials within the balloons are similar to fluids that are present during surgical dissection.
 - c. **Subject Debriefing**
Each surgeon will be told whether or not they ordered the balloons correctly right after they do so, and they will be asked to keep this information to themselves.

C. Documentation of Consent

- **Documenting Consent**
N/A
- **Waiver of Documentation of Consent (i.e., will not obtain subject's signature)**
Each subject will receive a Study Information Sheet

B. Removing a Subject

If a subject decides to cease participation we will shred their forms and choose a subsequent study subject.

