5.4 Secondary Use of the Data

[figure not shown]
N/A

Figure 1.

Conventional laparoscopic surgery (which inherently includes haptic feedback to the surgeon) versus robotic-assisted surgery (which does not)

Laparoscopic surgery

- 1-4 small incisions for insertion of instruments
- Small, rigid instruments with specific motions
- Surgeon operates standing in a traditional operating room arrangement
- Surgeon views operative field on a video screen
- Requires specialized training to develop expertise

Robotic-assisted surgery

- 1-4 small incisions for insertion of instruments
- Small instruments with wide range of motion and tremor control
- Ability to operate in very tight or small spaces
- Surgeon operates seated inside a specially designed console to control robotic instruments
- Surgeon views 3-D image of operative field
- Requires substantial specialized training to develop expertise

Figure 2.

The balloons - each filled with 20 mL of either air, water, petroleum jelly or water absorbing crystals (consistency of a non-ripe banana)

[figure not shown]

Figure 3.
Case Report Form 1
Surgeon Demographics

Subject # _____

Board Certification (circle all that apply) FACS FACOG FPMRS
Other _____

Age _____

Male Female non-Binary

Years since residency _____

Years since fellowship _____

Credentialed for robotic surgery Y N

Approximate total number of robotic cases performed _____

Figure 4.

Case Report Form 2

Study Data Collection

Subject # _____

Surgeon felt as though they could discern balloon contents using only sight? Y N

Balloon discernment via manipulation

HANDS

ROBOT

AIR

WATER

JELLY

CRYSTALS

Correct? Y N

Y N

Y N

Y N

If No, which did they think it was?

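### One balloon board for every surgeon, no stated re-ordering and immediate right/wrong feedback: the answer can reach later surgeons and may favour the robot group

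*Protocol*

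**What the plan says.** - **Instrument.** Protocol 1.7 (Study Instruments): "The same model will be used for all data collection if possible". A broken balloon may be swapped for an identical one. The four balloons are fixed to a poster board and surgeons may not detach them. Under Subject Identifiers, one key says which substance is in each balloon. No shuffling or rotation of positions is described.
- **Feedback.** Protocol 4.4 (Subject Debriefing): "Each surgeon will be told whether or not they ordered the balloons correctly right after they do so". The only safeguard is that "they will be asked to keep this information to themselves".
- **Uniformity.** Protocol 4.4 (Alternatives) explains why tissue is not used: "the study design calls for uniformity of the model objects".
- **Who is tested.** Protocol 4.1 draws Group A from board-certified surgeons on the hospital's staff. For Group B, "we will use any The Valley Hospital surgeons with unrestricted robotic privileges", or similarly credentialed surgeons met at the training centre, where 1.7 expects collection to take 1 or 2 days. The split of Group B between sites and the order of testing are not given.
- **Outcome and expectation.** Sections 1.3 and 1.6 make the primary outcome binary: all four balloons correct or not. Section 1.4: "The expectation is that group A will achieve 100% success".
- **Data form.** Case Report Form 2 (Figure 4) has a Y/N per substance and the prompt "If No, which did they think it was". It has no field for a board or an order.

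**The concern.** If the order stays the same, the whole answer is one sequence of four items that a surgeon can remember and repeat. Being told the order was right confirms it. A later surgeon who has heard it can score a success without discerning anything, and a binary all-correct outcome cannot tell the two apart.

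The direction matters. With Group A at its expected 100%, leakage has no room to act there. It can only lift Group B, which is the direction of the study's hypothesis. This does not require Group A to be tested first, because Group B surgeons can inform one another. If Group A falls short of 100%, both groups could rise, and the net effect would depend on testing order. Nothing on the forms records prior knowledge, so the bias could be neither detected nor corrected afterwards.

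**Working it through.** **The plan's own figure.** Section 1.4 gives the chance of a correct order as 1/24. Four contents can be arranged in 4! = 24 ways, and 1/24 = 0.0417, so the figure is right. It holds only for a surgeon with no prior knowledge of the order.

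**Inputs from the protocol.** Group A n = 35, Group B n = 18, expected Group A success 100% (1.4); chi-square test for categorical data (5.1).

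**Assumptions, not in the protocol.** True Group B success p = 0.80 or 0.70. Share L of Group B who know the order = 0, 10, 25 or 50%, which is 0, 1.8, 4.5 or 9 of 18. Informed surgeons are always correct. Group A scores 35/35.

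**Step 1: observed Group B rate** = p + (1 − p)L. For p = 0.80 and L = 0.25: 0.80 + 0.20 × 0.25 = 0.85.

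**Step 2: cut-offs against 35/35.**

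| Group B failures of 18 | Uncorrected chi-square p | Fisher p |
|---|---|---|
| 1 | 0.159 | 0.340 |
| 2 | 0.044 | 0.111 |
| 3 | 0.013 | 0.035 |

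The difference is non-significant at 0.05 with at most 1 failure by chi-square, or at most 2 by Fisher. At 2 failures the smallest expected count is 2 × 18/53 = 0.68, so the chi-square approximation is poor and both tests are shown.

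**Step 3: chance of a non-significant difference.** This is P(X ≤ 1) or P(X ≤ 2), where X is binomial with n = 18 and failure probability 1 − observed rate.

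| True p | L | Observed rate | Chi-square (≤ 1 failure) | Fisher (≤ 2 failures) |
|---|---|---|---|---|
| 0.80 | 0 | 0.80 | 9.9% | 27.1% |
| 0.80 | 10% | 0.82 | 13.9% | 34.6% |
| 0.80 | 25% | 0.85 | 22.4% | 48.0% |
| 0.80 | 50% | 0.90 | 45.0% | 73.4% |
| 0.70 | 0 | 0.70 | about 1% | about 6% |
| 0.70 | 10% | 0.73 | about 3% | about 10% |
| 0.70 | 25% | 0.775 | about 6% | about 19% |
| 0.70 | 50% | 0.85 | about 22% | about 48% |

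Non-significance is only a gauge. The protocol gives no non-inferiority margin and does not say that a non-significant test would establish non-inferiority.

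**Step 4: effect of the remedy.** Suppose there are four boards assigned at random, and an informed surgeon knows one order and otherwise discerns at 80%. With L = 0.25 the observed rate is 0.80 + 0.20 × 0.25/4 = 0.8125. The two probabilities become 12.3% and 31.7%, against 9.9% and 27.1% with no leak, and 22.4% and 48.0% with a single order.

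**The case against.** The strongest reply is that a fixed order is inferred from silence. The word identical describes the replacement balloons, not their positions. Case Report Form 2 scores by content, so it would work with a fixed or a changing order. That is fair: the protocol never says outright that the order is fixed. Still, one board with attached balloons, one key and no mention of re-ordering make a fixed order the natural reading. If the order did change, the form could not show which one a surgeon had faced.

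The route to Group B is also narrower than it first looks. Surgeons were asked to keep quiet, no reward for a correct answer is described, and a surgeon told that the order was wrong does not learn the right one. For surgeons met at the training centre, the likely source is another Group B surgeon who succeeded. These points lower the probable leak rate but do not remove the risk, since the request for secrecy is unenforced and cannot be checked. Feedback is a contributor, not the sole cause: a confident Group A surgeon knows the order without being told.

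The leak rates are assumptions, and having informed surgeons always correct is a worst case. At 10% leakage with p = 0.80, the observed rate moves only from 80% to 82%; the large shifts need a quarter to a half of Group B to be informed. This stands, and the figures show sensitivity, not expected bias.

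**Conclusion.** The concern holds. As written, the plan allows correct answers without discernment. If Group A performs as expected, the resulting bias runs toward non-inferiority of the robot. Its size cannot be fixed from the protocol. In the illustration, leakage to a quarter of Group B raises observed success by 5 percentage points when true success is 80% (80% to 85%) and by 7.5 points when it is 70% (70% to 77.5%). At 80% it roughly doubles the chance of a non-significant difference by either test.

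The conclusion rests on the order staying fixed, which is strongly suggested but not stated; the direction rests on Group A being at or near 100%. No passages contradict one another. This is a design weakness that is cheap to prevent and cannot be repaired later, so the change should be made before testing starts.

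**What to change.** - **Boards.** Prepare about four boards with the same balloons, volumes and materials but different orders, each with a code the surgeon cannot see.
- **Assignment.** Assign a board to each surgeon from a prepared random list covering both groups.
- **Recording.** Add the board code to Case Report Form 2. Check the answers against that code's key only after all four are written down.
- **Feedback.** Amend section 4.4 so that right/wrong results are held until collection at that site ends. Withholding feedback alone is not enough, because a confident surgeon already knows the order.

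**Cost.** A few more poster boards and balloons (1.7 already says replacements are easy to make), one form field and later feedback; no extra staff. No identifiers are collected, so surgeons would keep their subject number or be shown the key when the site closes. Several boards give up a little of the uniformity that 4.4 asks for. With 18 Group B surgeons over four boards (4 or 5 each), differences between boards could not be tested well, so all must be built to one specification. Re-positioning the balloons on a single board and recording the order would also limit leakage, at the cost of re-attaching them between surgeons.
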